2.3 Benefit/Risk Assessment

The potential long-term benefits of AMG 133 include anticipated weight loss and improved cardiovascular risk factors associated with weight loss. Potential risks of AMG 133, as anticipated from animal data and the literature, are described below in Section 2.3.2.

2.3.1 Key Benefits

There are no key anticipated benefits from short-term use of AMG 133.

2.3.2 Key Risks

Potential risks of AMG 133, as anticipated by evidence from animal data and the literature, include those commonly associated with biologics, including local (eg, injection site) reactions, systemic (eg, hypersensitivity) reactions and immunogenicity (ie, the development of anti-AMG 133 antibodies). Other potential risks include gastrointestinal tolerability issues and risks commonly associated with targeting obesity pathways.

Key potential risks are detailed below.

Gastrointestinal Tolerability Issues

Gastrointestinal tolerability issues including nausea, vomiting, and diarrhea are common adverse reactions for molecules targeting the obesity pathways. Gastrointestinal tolerability issues in humans are expected based on experience with marketed GLP-1R agonists. Subjects will be monitored for signs and symptoms of adverse events of nausea, vomiting, and diarrhea throughout the study.

Hypersensitivity Reactions

As with any biologic, administration of AMG 133 may result in systemic reactions including immune-mediated hypersensitivity. Drug hypersensitivity reactions typically occur during or within several hours after drug administration, but they may be delayed. Severe reactions may occur, including anaphylaxis, angioedema and serum-like sickness. Potential anaphylactic reactions will be assessed by Sampson criteria. If Sampson criteria are positive, the potential anaphylactic reaction will be confirmed by measuring tryptase in blood plasma within 30 minutes of symptoms, and at any other time points as warranted and if feasible. AMG 133 will be administered by SC or intravenous (IV) injection by a qualified clinical research staff member. Subjects will be monitored for signs and symptoms of hypersensitivity reactions during and after AMG 133 administration, such as fever, chills, shaking, hypotension, wheezing, itching, nausea, and/or rash.

Immunogenicity

As with all biological products, there is a potential for the development of anti-AMG 133 antibodies. The potential effects of anti-AMG 133 antibodies on subjects who might develop them are not known, but reduced efficacy of AMG 133 is a possibility. Subjects will be monitored for potential effects of antidrug antibodies (ADA) that may include antibody-mediated adverse events, altered drug exposure, or loss of efficacy. Pharmacokinetic and immunogenicity samples from subjects in this phase 1 study will be collected from study subjects at protocol defined intervals and analyzed to monitor the development of anti-AMG 133 antibodies. Positive samples will be titrated and evaluated for neutralizing antibodies. Additional blood samples may be obtained to evaluate any ADA mediated effects on safety, pharmacokinetics, and pharmacodynamics during the study.

[figure not shown]
Injection Site Reactions

Injection site reactions (eg, erythema, itching, hematoma, swelling, bruising, and pain) are common side effects of drugs with SC/IV administration. These reactions can range from mild to severe (including injection site necrosis, which is an uncommon side effect). After SC/IV administration, subjects will be monitored for injection site reactions, which may include redness, tenderness/pain, bruising, warmth, swelling, itching, and/or infection. If appropriate, photographic documentation of injection site reactions will be obtained.

The above benefit risk assessment supports the conduct of this clinical trial. Reference should be made to the investigator's brochure for further data on potential side effects of AMG 133.

3. Objectives and Endpoints

Objectives	Endpoints
Primary	

To assess the safety and tolerability of AMG 133 as single and multiple doses in subjects with obesity	
Subject incidence of treatment-emergent adverse events.Changes in laboratory safety tests, vital signs, and 12-lead electrocardiograms (ECGs)
Secondary	

To characterize the pharmacokinetics of AMG 133 as single or multiple doses in subjects with obesity	
AMG 133 pharmacokinetic parameters including, but not limited to, maximum observed drug concentration during a dosing interval (C_{max}), the time of maximum observed concentration (t_{max}), and area under the concentration-time curve (AUC)

To evaluate the immunogenicity of AMG 133	
Incidence of anti-AMG 133 antibody formation

Exploratory

Exploratory

3.1 Hypotheses

- AMG 133 will be safe and well tolerated following single and/or multiple SC dose administrations in subjects with obesity across the dose range evaluated
- AMG 133 PK profile following multiple SC dose administrations will support selection of dose and frequency of administration in future multi-dose trials of AMG 133

4. Study Design

4.1 Overall Design

Part A (cohorts 1 to 6 and cohort 11) is a phase 1, randomized, double-blind, placebo-controlled, SAD study in adult subjects with obesity. AMG 133 will be administered SC for cohorts 1 to 5 and cohort 11, and IV for cohort 6. Part A consists of a total of 7 cohorts.

Subjects will be confined at the Clinical Research Unit from check-in (morning of day -2) through the morning of day 8 for cohorts 1 to 5 and cohort 11 and, day 6 for cohort 6.

Approximately 56 subjects will enroll into 1 of 7 cohorts. In each cohort, 8 subjects will be randomized to receive AMG 133 or placebo SC (cohorts 1 to 5 and cohort 11) or IV (cohort 6) in a 3:1 ratio as described in [Table 7](#). For cohort 1, the first 2 subjects (sentinel pair) will be randomized such that 1 subject will receive AMG 133 and 1 subject will receive placebo. The sentinel pair will be observed for at least 48 hours before the remaining subjects in the cohort are dosed, provided there are no safety or tolerability concerns as assessed by the investigator. Enrollment into the SAD cohorts will be sequential. Subsequent cohorts will be dosed after the dosing regimen in the preceding cohort has been recommended by the Dose Level Review Team (DLRT) to be safe and

well tolerated based on the safety and laboratory data through at least day 15 for at least 7 out of 8 subjects dosed. Subjects in cohorts 1 to 5 and cohort 11 will also participate in [REDACTED] tests at day -1 and day 7.

Part B (cohorts 7 to 10) is a randomized, placebo-controlled, double-blind, MAD study in adult subjects with obesity. In each cohort, subjects will be randomized to receive AMG 133 or placebo SC in a 3:1 ratio as described in [Table 7](#). Approximately 24 subjects will enroll into cohorts 7 to 9. Cohorts 7 to 9 will include assessments of

[REDACTED] Enrollment into Part B cohort 7 will occur with a starting MAD dose that is at least 2 SAD dose levels below what was recommended by the DLRT to be safe and reasonably tolerated in Part A. Enrollment into the MAD cohorts 8 and 9 will be sequential.

Subjects in cohorts 8 and 9 will be dosed after the dose regimen in the preceding MAD cohort has been recommended by the DLRT to be safe and reasonably tolerated based on safety and laboratory data through at least study day 36 for 6 out of 8 subjects dosed. The DLRT for SAD cohort 11 will also make dosing recommendations for cohort 9

([Figure 1-1 \[A\]](#)). [REDACTED]

[REDACTED] All subjects in each Part B (MAD) cohort may be dosed on the same day.

Cohort 10 will enroll **up to** 20 subjects and will include the [REDACTED]

[REDACTED]. Therefore, the dose recommended for cohort 10 should be the same as a dose studied in a previous cohort.

The dose recommended for cohort 10 will depend on the final dose recommended for cohort 9 and the safety and tolerability profiles for MAD cohorts 7 and 8 ([Figure 1-1 \[B\]](#)).

In all dose escalation process, DRLM will make a recommendation and Amgen will make the final decision on dose level.

- MAD cohorts 7 to 9: Study drug will be administered every 4 weeks for a total of 3 SC doses. The dose levels will be defined after evaluation of the available PK and PD data from preceding cohorts in the SAD phase (Part A). Three different dose levels will be evaluated with the lowest dose administered to cohort 7, and 2 higher ascending doses administered to cohorts 8 and 9. The dose level for cohorts 7 to 9 will not exceed the highest dose evaluated in cohorts 1 to 6 and cohort 11 (Part A). Subjects enrolled in cohorts 7 to 9 will also be asked to [REDACTED]
- MAD cohort 10: Up to twenty subjects will be randomized in a 3:1 ratio to receive AMG 133 or placebo SC. All subjects will be asked to use [REDACTED]

[REDACTED] The dose level will not exceed the highest dose evaluated in cohorts 7 to 9 (Part B).

Part C (cohorts 12 to 13) is an open-label modified dose-escalation MAD study in subjects with obesity. Approximately 12 subjects (up to 6 subjects per cohort) will enroll in Part C and receive AMG 133 (see Table 7). Doses selected for these cohorts are known to have an acceptable safety and tolerability profile based on data reviewed by the DLRT from previous cohorts in Part A and Part B and will not exceed the dose levels previously studied in the MAD cohorts 7 to 9. Cohort 12 will receive [REDACTED] mg SC on days [REDACTED] followed by [REDACTED] mg SC on days [REDACTED] Cohort 13 will receive [REDACTED] mg on days [REDACTED] followed by [REDACTED] mg SC on days [REDACTED]. Cohorts 12 and 13 will enroll in parallel. The DLRT will review the safety and laboratory data through at least day 36.

Table 7. Planned Dose Levels by Cohort

	Cohort	No. Subjects	AMG 133/Placebo Dose/ Frequency	Route	N (active: placebo)
Part A	1	8	21 mg day 1	SC	6:2
	2	8	Not exceeding 70 mg day 1 ^a	SC	6:2
	3	8	Not exceeding 140 mg day 1 ^a	SC	6:2
	4	8	Not exceeding 280 mg day 1 ^a	SC	6:2
	5	8	Not exceeding 560 mg day 1 ^a	SC	6:2
	11	8	Not exceeding 840 mg day 1 ^a	SC	6:2
	6	8	Not exceeding 70 mg day 1 ^a	IV	6:2
Part B	7	8	Not exceeding 140 mg ^b Q4W x 3	SC	6:2
	8	8	Not exceeding 280 mg ^b Q4W x 3	SC	6:2
	9	8	Not exceeding 560 mg ^b Q4W x 3	SC	6:2
	10	≤ 20	Not exceeding 560 mg ^c Q4W x 3 +	SC	≤ 15:5
Part C	12	≤ 6		SC	N/A
	13	≤ 6		SC	N/A

N/A = not applicable; Q4W = every four weeks; SC = subcutaneous; IV = intravenous.

^a Actual dose levels will be based on available data from previous cohorts.

^b Dose will not exceed the highest dose evaluated in cohorts 1 to 5 and cohort 11 (Part A)

^c Dose will not exceed the highest dose evaluated in cohorts 7 to 9 (Part B)

The overall study design is described by a study schema in Section 1.2. The endpoints are defined in Section 3.

4.2 Number of Subjects

A total of approximately 112 subjects will be enrolled in the study. Approximately 56 subjects will be enrolled in Part A of the study, with 8 subjects in each of the 7 cohorts. Approximately 44 subjects will be enrolled in Part B of the study, with 8 subjects in cohorts 7 to 9 and up to 20 subjects in cohort 10. **Up to 12 subjects will be enrolled in Part C cohorts 12 to 13.** Additional subjects may be enrolled if a DLRT recommendation is made to expand, repeat, or add cohorts to the study **or if replacement subjects are needed.**

Subjects in this clinical investigation shall be referred to as “subjects.” For the sample size justification, see Section 9.2.

4.2.1 Replacement of Subjects

Subjects who withdraw from the study or who discontinue study drug administration prematurely may be replaced at the discretion of Amgen in consultation with the investigator. The replacement subject will be assigned to receive the identical treatment as the replaced subject.

4.2.2 Number of Sites

Approximately 1 to 3 investigative sites in United States will be included in the study. Sites that do not enroll subjects within 1 month of site initiation may be closed.

4.3 Justification for Investigational Product Dose

The planned cohort in this amendment of the study consists of a multiple-dose cohort following a titration schema as presented in [Figure 1-1](#).

Previously, subjects in Part A received single doses of AMG 133 - 21, 70, 140, 280, 560, and 840 mg administered SC. This part also consisted of an IV cohort (cohort 6) at a dose of 70 mg administered IV; **all SAD** have been completed. The starting dose and exposure multiples for the doses evaluated in SAD were calculated based on the NOAELs determined in the 13-week Good Laboratory Practices repeat-dose mouse and cynomolgus monkey nonhuman primate toxicology studies (every 2 weeks dosing, Section 2.2.2.3) and the observed reduction in body weight in the chronic efficacy study in obese cynomolgus monkeys.

Part B consisted of evaluation of AMG 133 **following repeat doses - 140, 280, and 420 mg administered Q4W for a total of 3 doses per cohort.** Preliminary review of the PK data in the FIH SAD **and MAD** part of the study demonstrated that AMG 133 pharmacokinetics follow a linear, dose proportional kinetics based on C_{max} (area under the curve [AUC] data pending), with a half-life of approximately **15 to 20 days**.

For **SAD cohorts 1 to 6 and 11**, no **serious adverse events** or deaths have been reported, and most **adverse events** reported were mild associated with nausea, vomiting, **and dyspepsia**. One subject in cohort 3 (140 mg dose) had a moderate adverse event associated with gastroenteritis **related to IP**. **Approximately 90% of subjects enrolled in MAD cohorts 7 to 10 reported mild GI-related adverse events (mainly nausea, vomiting, and diarrhea) after the first dose of AMG 133 and less than 5% experienced GI-related adverse events after the second dose.** There were **no serious adverse events or deaths reported after any of the doses**.

Approximately 26% of subjects in the MAD trial discontinued the study prior to

receiving the second dose which caused concerns regarding tolerability of the first dose; 50% of subjects in cohort 9 withdrew consent after receiving the 420 mg dose on day 1 due to GI-related adverse events. The doses were selected to allow for whole integer injection volumes to circumvent any potential dosing errors.

Part C consists of two cohorts (cohorts 12 and 13), both open-label to evaluate dose-level escalation from 70 mg to 420 mg. The objective of Part C is to evaluate first dose effects of AMG 133 on GI-related adverse events using a titration methodology. Cohort 12 will start at a lower dose [redacted] mg) of AMG 133 given [redacted]

Cohort 13 will start at a lower dose ([redacted] mg) of AMG 133 given [redacted]

The rationale for dose selection for Part C is based on the available PK data from this ongoing FIH study cohorts 1 to 11 (Part A and Part B) and the NOAEL exposures established based on 13-week GLP repeat-dose studies in mouse and cynomolgus monkeys.

Similarly, for cohort 12, the predicted human exposure multiples for intact AMG 133 following the second dose of [redacted] mg on Day [redacted] are approximately 40.5-fold and 45-fold for C_{max} and AUC_{ss} , respectively, based on NOAEL established in cynomolgus monkeys, and 43-fold and 42.4-fold for C_{max} and AUC_{ss} , respectively, based on NOAEL established in mice. The predicted human exposure multiples for total AMG 133 following the second dose of [redacted] mg on Day [redacted] are approximately 45-fold and 49-fold for C_{max} and AUC_{ss} , respectively, based on NOAEL established in cynomolgus monkeys, and 54-fold and 42-fold for C_{max} and AUC_{ss} , respectively, based on NOAEL established in mice (Table 8 and Table 9).

For cohort 13, the predicted human exposure multiples for intact AMG 133 following the second dose of [redacted] mg on Day [redacted] are approximately 39-fold and 43.2-fold for C_{max} and AUC_{ss} , respectively, based on NOAEL established in cynomolgus monkeys, and 41.3-fold and 40.6-fold for C_{max} and AUC_{ss} , respectively, based on NOAEL established in mice. The predicted human exposure multiples for total AMG 133 following the second dose of [redacted] mg on

Day █ are approximately 42.2-fold and 45.5-fold for C_{max} and AUC_{ss} , respectively, based on NOAEL established in cynomolgus monkeys, and 50.9-fold and 47.5-fold for C_{max} and AUC_{ss} , respectively, based on NOAEL established in mice (Table 8 and Table 9).

Table 8. Estimated Exposure Margins of Intact AMG 133 Following Repeat Doses (Q4W)

Clinical Dose (mg)	Route	Predicted Human Exposure		Predicted Exposure Multiples ^a			
		AUC ₀₋₂₈ (μ g·hr/mL)	C_{max} (μ g/mL)	Mouse ^b		Monkey ^c	
█ (cohort 12) ^f	SC	17 731	37	42.4	43	45.1	40.5
█ (cohort 13) ^f	SC	18 513.6	38.5	40.6	41.3	43.2	39

AUC = area under the concentration-time curve; AUC_{last} = area under the concentration-time curve during a last dosing interval; AUC_{0-28} = area under the concentration-time curve during a dosing interval defined here from time 0 to 28 days after the 2nd dose; C_{max} = maximum observed drug concentration during a dosing interval defined here after the 2nd dose; FIH = First in Human; NOAEL = no observed adverse effect level; PK = pharmacokinetic; SC = subcutaneous; Q4W = every 4 weeks.

^a PK data from AMG 133 FIH study is used for PK prediction

^b After the last dose after 13 weeks of treatment (7 total doses) at the NOAEL dose of 150 mg/kg in mice (Study 150238); mean AUC_{last} ($AUC_{0-168hrs}$) of 188 000 μ g·hr/mL and mean C_{max} of 1590 mg/mL of Intact AMG 133.

^c After the last dose after 13 weeks of treatment (7 total doses) at the NOAEL dose of 120 mg/kg in cynomolgus monkeys (Study 150239); mean AUC_{last} ($AUC_{0-168hrs}$) was 200 000 μ g·hr/mL and mean C_{max} of 1500 mg/mL of Intact AMG 133.

^d AUC exposure multiples = ratio of AUC_{last} after 13 weeks (7 doses) of AMG 133 administration in the mouse or monkey x 4/predicted AUC_{0-28} in humans after the 2nd dose.

^e C_{max} multiple = the ratio of C_{max} after the last dose after 13 weeks (7 doses) of AMG 133 in the mouse or monkey to the predicted C_{max} for each human single dose.

^f Actual dose levels will be based on available data from previous cohorts.

Source: Report 153788

Table 9. Estimated Exposure Margins of Total AMG 133 Following Repeat Doses (Q4W)

Clinical Dose (mg)	Route	Predicted Human Exposure		Predicted Exposure Multiples ^a			
		AUC _{tau} (μ g·hr/mL)	C_{max} (μ g/mL)	Mouse ^b		Monkey ^c	
█ (cohort 12) ^f	SC	22 831	43.5	51	54.3	48.9	45.1
█ (cohort 13) ^f	SC	24 504	46.4	47.5	50.9	45.5	42.2

AUC = area under the concentration-time curve; AUC_{0-28} = area under the concentration-time curve during a dosing interval defined here from time 0 to 28 days after the 2nd dose; C_{max} = maximum observed drug concentration during a dosing interval defined here after the 2nd dose; FIH = First in Human; NOAEL = no observed adverse effect level; PK = pharmacokinetic; SC = subcutaneous; Q4W = every 4 weeks.

^a PK data from AMG 133 FIH study is used for PK prediction

^b After the last dose after 13 weeks of treatment (7 total doses) at the NOAEL dose of 150 mg/kg in mice (Study 150238); mean AUC_{last} (**AUC_{0-168hrs}**) of 291 000 µg hr/mL and mean C_{max} of 2360 mg/mL of Total AMG 133.

^c After the last dose after 13 weeks of treatment (7 total doses) at the NOAEL dose of 120 mg/kg in cynomolgus monkeys (Study 150239); mean AUC_{last} (**AUC_{0-168hrs}**) was 279 000 µg hr/mL and mean C_{max} of 1960 mg/mL of Total AMG 133.

^d AUC exposure multiples = ratio of AUC_{last} after 13 weeks (7 doses) of AMG 133 administration in the mouse or monkey x 4/predicted (**AUC_{0-28 days}**) in humans after the **2nd** dose.

^e C_{max} multiple = the ratio of C_{max} after the last dose after 13 weeks (7 doses) of AMG 133 in the mouse or monkey to the predicted C_{max} for each human single dose.

^f Actual dose levels will be based on available data from previous cohorts.

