Part C: Cohorts 12 - 13: Subjects who meet all the screening inclusion criteria and none of the exclusion criteria will be eligible to report to the research facility once on day -2 (up to day -4), at which time assessments will be performed to confirm eligibility. If subjects are eligible after the completion of all day -2 assessments, subjects will receive AMG 133 on day 1.

Day -1

Part A: Cohorts 1 to 5 and cohort 11: A [REDACTED] test will be performed on day -1 along with additional procedures as outlined in the Schedule of Activities in **Section 1.3.** As part of the [REDACTED]

summarized in the Schedule of Activities in **Section 1.3**. [REDACTED] tests will not be performed in cohort 6.

Part B: cohorts 7 to 10: Subjects who meet all the screening inclusion criteria and none of the exclusion criteria will be eligible to report to the research facility on day -1, at which time assessments will be performed to confirm eligibility. If subjects are eligible after the completion of all day 1 assessments, subjects will be randomized to receive either AMG 133 or placebo on day 1.

Day 1:

Part A: After completion of all predose procedures on the day of dosing (day 1), subjects will receive investigational product (SC for cohorts 1 to 5 and cohort 11 and IV for cohort 6, only). Subjects will undergo vital signs and pharmacokinetics blood draws postdose as outlined in the Schedule of Activities in **Section 1.3**.

Part B: After completion of all predose procedures on the day of dosing (day 1), subjects will receive investigational product (SC for cohorts 7 to 10). Subjects should undergo additional vital sign assessments 3 hours after dosing but are not scheduled to get postdose blood draws on day 1 (see Schedule of Activities in **Section 1.3**).

Part C: After completion of all predose procedures on the day of dosing (day 1), subjects will receive AMG 133 (SC). Subjects are scheduled to get postdose blood draws on day 1 but should undergo additional monitoring (per clinical site standard operating procedures) and vital sign assessments approximately 4 to 5 hours after dosing. The subjects can be discharged from the clinical facility based upon a stable vital signs and assessment per clinical site standard operating procedures.

Day 7

Cohorts 1 to 5 and cohort 11: A [REDACTED] test will be repeated on day 7 along with additional procedures as outlined in the Schedule of Activities in **Section 1.3**.

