Please note: Subjects will be admitted after confirmed eligibility on day -1 for a 3 day (2 night) residency. Subjects will be dosed on day 1, the second day of residency. Subjects will be admitted on days 28 – 30 and days 56 – 58 for a 3 day (2 night) residency. Subjects will receive AMG 133 or placebo on days 29 and 57, respectively.

^a Upon permanent discontinuation from the study treatment for any reason, a safety follow-up visit will be performed approximately 30 (+3) days after the end of the last dosing interval of investigational product.

^b Physical exam to include neurologic assessment.

^c Predose assessment.

^d 12-lead ECGs to be performed in a standardized method, in triplicate, and run consecutively (all 3 ECGs should be completed within a total of 5 minutes from start of the first to the completion of the third).

^e Single 12-lead ECG.

^f 3 sets of triplicate 12-lead ECGs at baseline (day 1 predose).

^g Subjects should get vital signs 3 hours after dosing

^h Analyzed at the local laboratory, additional samples may be collected for safety reasons, at the investigator's discretion.

ⁱ 10-hour fasting is required at all time points.

^j Additional on-treatment pregnancy testing may be performed at the investigator's discretion if there is suspicion that a female subject is pregnant or per local laws and regulations.

^k Analyzed at the central laboratory/sponsor facility, additional samples may be collected for safety reasons, at the investigator's discretion.

^m Local laboratory at screening, then central laboratory at other time points.

ⁿ For subjects who provided informed consent for the pharmacogenetic studies

Table 4. Schedule of Activities – Cohort 10

PROCEDURE	Screening			Treatment Period												EOS/SFU ^a			Notes						
	Study Day			-28	-14	-1	1	5	7	15	22	29	36	43	50	57	63	71	78	85	127	155	169	207	
	Visit Windows						± 1 day			± 1 day			± 1 day			± 3 day			± 7 day						
GENERAL AND SAFETY ASSESSMENTS																									
Informed consent	X																								
Inclusion and exclusion criteria	X																								
Demographics	X																								
Medical history	X																								
Substance use history	X																								
Physical examination ^b	X	X																		X	X			X	
Height and body mass index	X																								
Body weight (kg)	X							X	X	X	X	X	X	X	X	X	X	X	X	X	X	X	X	X	
Waist circumference (cm)								X	c				X	c						X	X				X
C-SSRS + PHQ9	X	X																							

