Please note: Subjects will be admitted after confirmed eligibility on day -1 for a 3 day (2 night) residency. Subjects will be dosed on day 1, the second day of residency. Subjects will be admitted on days 28 – 30 and days 56 – 58 for a 3 day (2 night) residency. Subjects will receive AMG 133 or placebo on days 29 and 57, respectively.

^a Upon permanent discontinuation from the study treatment for any reason, a safety follow-up visit will be performed approximately 30 (+3) days after the end of the last dosing interval of investigational product.

^b Physical exam to include neurologic assessment.

^c Predose assessment.

^d 12-lead ECGs to be performed in a standardized method, in triplicate, and run consecutively (all 3 ECGs should be completed within a total of 5 minutes from start of the first to the completion of the third).

^e Single 12-lead ECG.

^f 3 sets of triplicate 12-lead ECGs at baseline (day 1 predose).

^g Analyzed at the local laboratory, additional samples may be collected for safety reasons, at the investigator's discretion.

^h 10-hour fasting is required at all time points.

ⁱ Additional on-treatment pregnancy testing may be performed at the investigator's discretion if there is suspicion that a female subject is pregnant or per local laws and regulations.

^j Analyzed at the central laboratory/sponsor facility, additional samples may be collected for safety reasons, at the investigator's discretion.

^m Local laboratory at screening, then central laboratory at other time points.

ⁿ For subjects who provided informed consent for the pharmacogenetic studies.

^p Subjects should get vital signs 3 hours after dosing

Table 5. Schedule of Activities – Part C Cohort 12

PROCEDURE	SCREENING		TREATMENT PERIOD							SFU/EOSA	
	-28	-2 ^b	1	8	15	20	43	57	71	132	193
Study Day											
Visit Windows								± 1 day		± 3 days	±7 days
Visit type	C	C	C	C	C	C	C	P	C	P	C
GENERAL AND SAFETY ASSESSMENTS											
Informed consent	X										
Inclusion and exclusion criteria	X										
Demographics	X										
Medical history	X										
Substance use history	X										
Physical examination ^c	X	X						X		X	X
Height and body mass index	X										
Body weight (kg)	X		X ^d	X ^d	X ^d	X	X ^d		X		X
Waist circumference (measured in cm only)			X ^d				X ^d		X		X
C-SSRS + PHQ9	X		X ^d	X ^d	X ^d		X ^d		X		X
ECG triplicate measurement	X ^e	X ^e	X ^{d,f,g}				X ^{d,f}		X ^f		
Vital signs (BP, HR, RR, Temp)	X	X	X ^{d,h}	X ^{d,h}	X ^{d,h}	X	X ^{d,h}		X		X

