Adverse events			X	X	X	X	X	X ⁱ	X	X ⁱ	X
Serious adverse events	X	X	X	X	X	X	X	X ⁱ	X	X ⁱ	X
Concomitant therapies review	X	X	X	X	X	X	X	X ⁱ	X	X ⁱ	X

STUDY TREATMENT											
Amgen investigational product											
LABORATORY ASSESSMENTS											
Coagulation ^j	X	X									
Hematology ^j	X	X		X	X	X	X		X		X
Chemistry ^j	X	X		X	X	X	X		X		X
HS-CRP ^j			X						X		X
HIV, Hepatitis B and C screening ^j	X										
Serum amylase and lipase ^j			X	X	X	X	X		X		X
eGFR ^j	X	X									X
Urinalysis ^j	X	X							X		X
Alcohol, cotinine, and drug screen ^j	X	X									

Page 1 of 2

Footnotes defined on last page of the table.

Table 5. Schedule of Activities – Part C Cohort 12

PROCEDURE	SCREENING		TREATMENT PERIOD							SFU/EOSA		
	Study Day	-28	-2 ^b	1	8	15	20	43	57	71	132	193
Visit Windows							± 1 day		± 3 days		± 7 days	
Visit type	C	C	C	C	C	C	C	P	C	P	C	
Serum and/or Urine pregnancy test (females only) ^j	X	X										X
Serum FSH test ^j (postmenopausal females only)	X											
Anti-AMG 133-antibody ^{k,m}			X ^d		X ^d		X ^d		X			X
STUDY-SPECIFIC ASSESSMENTS (eg, DISEASE-SPECIFIC ASSESSMENTS, RADIOLOGICAL ASSESSMENTS)												
PHARMACOKINETIC ASSESSMENTS												
Plasma AMG 133 pharmacokinetics ^{k,m}				X ^d	X ^d	X ^d		X ^d		X		X
PHARMACODYNAMIC ASSESSMENTS												

PHARMACOGENETIC ASSESSMENTS											
Pharmacogenetic studies ^{o,m}											
IMAGING				X							

Page 2 of 2

BP = blood pressure; C = clinic visit; C-SSRS = Columbia Suicide Severity Rating Scale; cm = centimeters; [REDACTED];
[REDACTED]; ECG = electrocardiogram; eGFR = estimated glomerular filtration rate; EOS = end of study;

FSH = follicle stimulating hormone:

[REDACTED] HIV = human immunodeficiency virus; HR = heart rate; HS-CRP = high-sensitivity C-reactive protein;
[REDACTED] p = phone visit; PD = pharmacodynamic; PHQ9 = Patient Health Questionnaire-9; RR = respiratory rate;
[REDACTED]; SFU = safety follow-up; Temp = temperature.

Please note: Subjects are eligible for an optional in-house residence period on Day 1 and 8 for an overnight observation period. Subjects are eligible for a required in-house residency period for Day 15 and 43. Subjects will receive AMG 133 on Days 1, 8, 15, and 43.

^a Upon permanent discontinuation from the study treatment for any reason, an SFU visit will be performed approximately 30 (+3) days after the end of the last dosing interval of investigational product.

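### After the first dose, Part C schedules no adverse event contact between day 1 and day 8, whereas Part B had residency to day 2 and two or three visits by day 7, so first-dose GI rates in the two parts are not collected alike

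*Protocol*

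**What the plan says.** Protocol section 4.3 gives the purpose of Part C: "The objective of Part C is to evaluate first dose effects of AMG 133 on GI-related adverse events using a titration methodology". The same section motivates it from Part B: "Approximately 90% of subjects enrolled in MAD cohorts 7 to 10 reported mild GI-related adverse events" after the first dose, and "50% of subjects in cohort 9 withdrew consent after receiving the 420 mg dose on day 1 due to GI-related adverse events".

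**Part C after the first dose.** In the synopsis, vital signs are taken about 4 to 5 hours after dosing, and then: "The subjects can be discharged from the clinical facility based upon a stable vital signs and assessment per clinical site standard operating procedures". The Table 5 note for cohort 12 says: "Subjects are eligible for an optional in-house residence period on Day 1 and 8 for an overnight observation period". The Table 6 note offers the same option to cohort 13 on days 1, 8, 15 and 22. The on-study days in Table 5 are "1 8 15 20 43 57 71 132 193", and the adverse event row is marked from day 1 onward ("Adverse events X X X X X"). Nothing is scheduled between day 1 and day 8. Table 6 has the same gap.

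**Part B after the first dose.** The notes to Tables 3 and 4 say: "Subjects will be admitted after confirmed eligibility on day -1 for a 3 day (2 night) residency". Dosing falls on the second day of that stay, so it runs through day 2. The next adverse event visits are days 4, 5 and 7 for cohorts 7 to 9 (Table 3) and days 5 and 7 for cohort 10 (Table 4).

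**Collection rules for both parts.** Adverse events are reportable continuously from the first dose (section 8.2.3.1.1). Open-ended questioning is the preferred method (section 8.2.3.2). Onset and resolution dates are recorded (Appendix 4).

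**The concern.** Subject incidence of an adverse event depends partly on how often and how soon subjects are asked. The events at issue are nausea, vomiting and diarrhea, described in section 4.3 as mild. A mild, short episode on day 2 or 3 is more likely to be mentioned to staff during residency or at a visit on day 4 or 5 than at a first contact on day 8.

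This falls on the question Part C was added to answer. If its first-dose GI rate comes out below about 90%, part of the gap could reflect fewer contacts, and the incidence data alone could not say how much.

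The optional overnight stay does not close the gap. The synopsis lists its triggers as vital sign changes, events that interfere with daily activities, and investigator judgement. Appendix 4 defines moderate severity by interference with usual activity and mild as easily tolerated. The stay is therefore aimed at more symptomatic subjects than those with the mild events in question.

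**Working it through.** **1. The plan's own figure.** The schedules give no capture rate. The only related figure is the detection statement in protocol section 9.2 and SAP section 3.2, and it reproduces: 1 − 0.97^87 = 0.929 and 1 − 0.95^87 = 0.988. It assumes that every event that occurs is recorded.

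**2. Scheduled adverse event contacts after the first dose (Tables 3 to 6; dosing day not counted).**

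| Cohorts | Scheduled stay after dosing | Visits on days 2 to 7 | Visits within 28 days |
|---|---|---|---|
| 7 to 9 | to day 2 | 4, 5, 7 = 3 | 4, 5, 7, 15, 22, 29 = 6 |
| 10 | to day 2 | 5, 7 = 2 | 5, 7, 15, 22, 29 = 5 |
| 12 | optional night | none = 0 | 8, 15, 20 = 3 |
| 13 | optional night | none = 0 | 8, 15, 22, 29 = 4 |

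Day 2 in Part B is a residency day, not a column in Tables 3 or 4, so it is not counted as a visit.

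**3. After the first step-up dose** (day 15 in cohort 12, day 29 in cohort 13). An overnight stay is required. Scheduled contacts in the next 28 days are days 20 and 43, or days 34 and 57: 2 in each cohort, against 6 or 5 after Part B's first dose.

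**4. What weaker capture could do: illustration only.** Assumptions, none from the documents: the true rate stays at 90% (no titration effect), Part B captured everything, each affected subject has k episodes, and each episode is reported independently with probability s. Then

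observed subject incidence = 0.90 × [1 − (1 − s)^k].

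Worked case, s = 0.7 and k = 2: 0.90 × (1 − 0.09) = 0.819. The second figure in each cell is the binomial probability that 8 or fewer of 12 Part C subjects report a GI event.

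| s | k = 1 | k = 2 | k = 3 |
|---|---|---|---|
| 1.0 | 90%; 2.6% | 90%; 2.6% | 90%; 2.6% |
| 0.9 | 81%; 18.0% | 89.1%; 3.4% | 89.9%; 2.6% |
| 0.7 | 63%; 70.5% | 81.9%; 15.8% | 87.6%; 5.2% |
| 0.5 | 45%; 96.4% | 67.5%; 58.3% | 78.8%; 24.0% |

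A spurious improvement is possible. Its size rests wholly on s and k: with several episodes per subject and moderate recall it nearly vanishes, and with one episode and poor recall it is large.

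**The case against.** The strongest case on the other side has five parts.

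- **Collection in week 1 is not absent.** A reader might infer that Part C asks about adverse events only at day 8. The documents do not support that: day 1 is marked, there is a 4 to 5 hour postdose check, and subjects may stay overnight. Reporting is continuous and events are dated, so an episode on day 3 can be recorded at the day 8 clinic visit. Ascertainment is weaker, not missing.
- **Part B is not uniform.** Cohort 10, up to 20 of 44 subjects, has no day 4 visit, and the 90% figure pools cohorts 7 to 10. The contrast is 3 or 2 visits against 0.
- **Other evidence depends little on visit density.** Section 4.3 also rests on consent withdrawal in cohort 9 and on about 26% of MAD subjects stopping before the second dose. The SAP tabulates discontinuation reasons and adverse events leading to withdrawal of investigational product. Open-label reporting could also raise Part C counts.
- **No formal comparison is planned.** No hypotheses are tested, and protocol section 9.4.2.1 summarizes Part C separately. Part C also starts at a lower dose by design, so a raw first-dose contrast mixes dose with contact schedule in any case.
- **Redaction.** A symptom tool may sit among the blacked-out assessments.

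All of this stands as a limit on the claim. None of it removes the asymmetry. SAP sections 9.6.1 and 9.6.2 report adverse events by dose phase, with Parts B and C together as the MAD phase, and by actual treatment group. Nausea and vomiting are an event of interest. The Part B and Part C incidences will therefore be read within one phase, and Table 9-1 plans no sensitivity analysis.

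**Conclusion.** The difference in scheduled contact is established from the protocol's own tables: on days 2 to 7 after the first dose, 3 or 2 visits plus residency to day 2 in Part B, and no visit plus an optional night in Part C. It bears directly on Part C's stated objective, so reading Part C's GI incidence against Part B's roughly 90% is open to differential ascertainment that could favour titration.

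A reader might go further and infer that titration will look better through ascertainment alone, or that the bias must run that way. The documents do not show either. They give no recall figure, events can be recalled at day 8, open-label reporting may act in the opposite direction, and withdrawal data offer a partly independent view of tolerability. The size and net direction of the bias are unknown.

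The conclusion assumes that no redacted assessment collects GI symptoms between day 1 and day 8. It warrants a cheap correction to the schedule or, failing that, disclosure. It does not invalidate Part C.

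**What to change.** In Tables 5 and 6, add adverse-event-only contacts using the existing phone visit type on Part B's contact days after the first dose, for example days 2, 5 and 7. Use the same open-ended question as in Part B. Add contacts at the same intervals (1, 4 and 6 days after dosing) after the first step-up dose where no visit already exists: days 16, 19 and 21 in cohort 12, and days 30, 33 and 35 in cohort 13. The morning after the required overnight stay can serve as the first of these, and the day 20 or day 34 clinic visit may make another unnecessary.

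The documents do not give Part C's enrolment status. If subjects are already past these points, state in the SAP that Part B and Part C GI incidences were collected with different contact intensity and should not be compared directly.

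Cost: 3 calls × 12 subjects = 36 short calls after the first dose, at most the same again after the step-up (2 × 12 = 24 if the overnight discharge serves as one contact), and an edit to two schedule tables. A phone call only partly matches in-clinic contact, so some difference will remain and should be acknowledged in the report.
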